## Background

Atopic dermatitis (AD) is a common skin disease that is characterized by chronic, relapsing skin inflammation and eczematous, itchy lesions (Beiber, 2008). The prevalence of AD has increased over the past few decades, with 15-30% of children and 2-10% of adults being affected (Williams & Flohr, 2006). The pathogenesis of AD is as a result of a complex interaction between the epidermal barrier, the immune system and pruritus, with each factor contributing to disease initiation and progression (Kabashima, 2013). As the epidermal barrier breaks down in skin of AD patients, allergens are exposed to the underlying antigen presenting cells (APC's). Primed APC's migrate to local lymph nodes and activate naive T cells to Th2 cells. Th2 cells then traffic to the AD lesion and promote eosinophilic inflammation through release of Th2 cytokines (IL-4, IL-13, IL-25) and TSLP (Peng & Novak, 2015). Immune cells such as eosinophils, mast cells, basophils, innate lymphoid cells (IL-C2s) and dendritic cells infiltrate into the AD lesion, while circulating Th2 cells cause an increase in IgE and eosinophils in serum (Leung et al, 2004).

Interleukin-5 (IL-5) is a key cytokine involved in the differentiation and maturation of eosinophils from hematopoietic stem cells in the bone marrow, their mobilization and migration from the bone marrow to the blood, and their activation and survival in tissue (Blanchard and Rothenberg, 2009). The receptor for IL-5 (IL-5R $\alpha$ ) is expressed on eosinophils and basophils, but may also be expressed on other recently identified cells, such as innate lymphoid type 2 cells (ILC2).

There is evidence that in chronic allergic inflammatory diseases, eosinophilia may arise as a result of (i) the recruitment of mature cells from the periphery in response to locally elaborated chemoattractants such as eotaxin (Wardlaw et al., 1999) and/or (ii) the localized maturation of eosinophil lineage-committed progenitors, termed "*in situ* differentiation" in the presence of locally elaborated cytokines namely IL-5 (Sehmi et al., 2000; Sehmi et al., 2016). It is now apparent that type 2 innate lymphoid cells are an important source of IL-5 in mucosal tissue promoting eosinophilic inflammation including the skin in atopic dermatitis (Kim et al., 2013; Bonefeld et al., 2016). The aim of the current study is to target the local eosinophilopoietic process by interfering with the IL-5/IL-5R $\alpha$  signaling axis. Our previous and ongoing studies show that eosinophils, basophils, eosinophil progenitor cells and innate lymphoid type 2 cells

express IL-5R $\alpha$  and may be a target population for benralizumab, a humanized afucosylated antibody directed against IL-5R $\alpha$  subunit.

## **Hypothesis**

In atopic dermatitis, local IL-5 driven eosinophilopoietic processes contribute to development of tissue eosinophilia. Targeting the IL-5/ IL-5R $\alpha$  axis will attenuate eosinophilic inflammation in the skin.

## **Study design**

This randomized, double-blind, parallel group, placebo-controlled study will evaluate the effect of 3 doses of a fixed 30 mg dose of benralizumab administered subcutaneously (SC) every 4 weeks to patients with moderate-to-severe atopic dermatitis, on the severity of atopic dermatitis, and the cellular inflammation of skin lesions in these patients.

### *Screening and Baseline*

During a screening period (Days -1 to 0), patients with moderate-to-severe atopic dermatitis who develop late phase cutaneous response following intradermal allergen challenge, will be recruited for the study.

### *Effect of treatment on clinical disease*

Skin lesions will be graded using validated scales before the start of treatment, and throughout the study to assess the effect of benralizumab on changes to the severity of disease. Biopsies from skin lesions and samples of peripheral blood will be examined for levels of cells that express IL-5R $\alpha$  subunit including eosinophils, basophils, eosinophil progenitor cells, and innate lymphoid type 2 cells using flow cytometry. In addition, methylcellulose colony forming assay will be used to enumerate the IL-5 driven clonogenic potential of progenitor cell populations within the blood.

[figure not shown]
### *Effect of treatment on allergen-induced responses*

An intradermal allergen challenge will be conducted 1 week after the last dose of study drug to determine the effect of benralizumab on allergen-induced responses in skin. The size of the resulting skin wheal will be measured at 24h post-challenge. Biopsies of the skin wheal will be obtained for measurements of eosinophils and basophils per mm^2 tissue using standard

histochemical and immuno-histochemical stains. Additional biopsies of the skin wheal will be collected to measure the frequency of eosinophils, basophils, eosinophil progenitor cells, and innate lymphoid type 2 cells by flow cytometry.

#### *Follow-up*

Patients will return for a safety follow-up visit on study Day 140 (week 20), which is 12 weeks after the last dose/11 weeks after the last study procedure.

*Figure 1 - Study flow chart.*

Randomized double-blind, placebo-controlled, parallel-group prospective study. Patients with a history of atopic dermatitis will enter a screening period to assess responses to intradermal allergen challenge. Those developing a late cutaneous response 24 hours later will have the size of the wheal/flare measured and a punch biopsy obtained from the challenge site for measurement of eosinophils and basophils. Patients will then be randomized 1:1 to benralizumab (30 mg SC monthly) or placebo, with dosing at days 0, 28 and 56. Blood and a sample of a skin lesion will be collected on Day 0 before dosing. A skin lesion will be collected at Day 28 and blood will be collected again 65 days after the first dose, for assessments of eosinophils, basophils and other cells including eosinophil progenitors, ILC2s, hemopoietic progenitor cells and CD4+ T cells. On Day 64 an intradermal allergen challenge will be conducted and on Day 65 the size of the wheal/flare will be measured and a punch biopsy will be obtained from the challenge site for a measurement of eosinophils and basophils. Skin lesions will be assessed clinically before dosing and throughout the study using the EASI score. A safety follow up visit will take place at week 20, which is 140 days after the first dose (12 weeks after the last dose). Each visit has a +/- 3 day window with the exception of Day 0 and Day 65 which must take place exactly 1 day after Day -1 and Day 64, respectively.

#### **Duration of the study**

The total length of a patient's participation in the trial is up to 25 weeks;

- up to 4 weeks screening period
- 8 weeks treatment period
- 1 week post-treatment period

- 12 weeks follow-up

### **Study period**

Estimated date of first subject enrolled Q4 2017

Estimated date of last subject completed Q2 2019

### **Blinding**

This study will be a double-blind study, using a placebo. The placebo will have an appearance identical to that of drug. The staff who administers the treatment, any study staff involved in subject evaluations, and the subjects, will remain blinded to treatment assignment for the duration of the study.

### **Study Objectives**

#### *Primary Objective:*

The primary objective is to evaluate the effect of benralizumab on the allergen-induced number of eosinophils in the skin assessed by histological examination on Day 65, at 24h post-intradermal allergen challenge, compared to placebo. Intradermal saline challenge will be used as a control.

#### *Secondary Objectives:*

The secondary objectives are to evaluate the effect of benralizumab on (i) the allergen-induced number of basophils in the skin, as assessed by immuno-histochemical staining of a biopsy of the skin wheal collected on Day 65, at 24h post-intradermal allergen challenge, compared to placebo, (ii) the allergen-induced late phase cutaneous response by measuring the skin wheal on Day 65, at 24h post-intradermal allergen challenge, compared to placebo, and (iii) on disease severity at 65 days post-treatment, by assessing skin lesions using the Eczema Area and Severity Index (EASI) score, compared to placebo.

#### *Exploratory Objectives:*

The exploratory objectives are to evaluate the effect of benralizumab on the number of eosinophils, basophils, eosinophil progenitor cells and innate lymphoid type 2 cells, CD4+ T cells and hemopoietic cells in skin lesions on Day 28 post-treatment, compared to placebo.

Comparisons of local versus systemic drug-induced changes will be made by making similar cellular assessments in the blood on Day 65. In addition, we will prepare methylcellulose cell cultures from samples of Day 65 peripheral blood to enumerate the out-growth potential of the circulating eosinophil/basophil progenitor cell population.

### **Selection of Study Population**

Men and women, 18 to 65 years of age, with moderate-to-severe atopic dermatitis, whose disease cannot be adequately controlled with, and agree to withhold, topical/oral anti-inflammatory medications. The total enrollment for the study will be sufficient to result in 20 evaluable subjects. Any patients dropping out of the study prior to primary outcome assessment will be replaced.

### **Inclusion Criteria**

The following inclusion criteria must be met for to enter the screening phase of the study:

1. Male and female patients 18 through 65 years of age.
2. Women of childbearing potential (WOCBP) must not be actively seeking pregnancy, and must use an effective form of birth control (confirmed by the Investigator). Effective forms of birth control include: true sexual abstinence, a vasectomized sexual partner, Implanon, female sterilization by tubal occlusion, any effective IUD intrauterine device/IUS levonorgestrel Intrauterine system, Depo-Provera™ injections, oral contraceptive, and Evra Patch™ or Nuvaring™. WOCBP must agree to use effective method of birth control, as defined above, from enrolment, throughout the study duration and within 16 weeks after last dose of IP. They must demonstrate a negative serum pregnancy test at screening and demonstrate a negative urine pregnancy test immediately before each dose of study drug or placebo. Women not of childbearing potential are defined as women who are either permanently sterilized (hysterectomy, bilateral oophorectomy, or bilateral salpingectomy), or who are postmenopausal. Women will be considered postmenopausal if they have been amenorrheic for 12 months prior to the planned date of randomization without an alternative medical cause. The following age-specific requirements apply:

- Women <50 years old would be considered postmenopausal if they have been amenorrheic for 12 months or more following cessation of exogenous hormonal treatment and follicle stimulating hormone (FSH) levels in the postmenopausal range.
- Women ≥50 years old would be considered postmenopausal if they have been amenorrheic for 12 months or more following cessation of all exogenous hormonal treatment.

3. All male patients who are sexually active must agree to use an acceptable method of contraception (condom with or without spermicide, vasectomy) from the first dose of IP until 16 weeks after their last dose.
4. General good health
5. Moderate to severe atopic dermatitis
6. Able to understand and give written informed consent and has signed a written informed consent form approved by the investigator's REB

The following inclusion criteria must be met for entry into the dosing phase of the study:

1. Positive skin-prick test to common aeroallergens (including cat, dust mite, grass, pollen)
2. Positive late cutaneous response to intradermal allergen challenge

### **Exclusion Criteria**

Patients should not enter the study if any of the following exclusion criteria are fulfilled:

1. History of anaphylaxis to any biologic therapy or vaccine
2. History of clinically significant hypotensive episodes or symptoms of fainting, dizziness, or light headedness, as judged by the investigator
3. Any history or symptoms of clinically significant cardiovascular disease, particularly coronary artery disease, arrhythmias, hypertension, or congestive heart failure
4. Any history or symptoms of clinically significant neurologic disease, including transient ischemic attack (TIA), stroke, seizure disorder, or behavioral disturbances
5. Any history or symptoms of clinically significant autoimmune disease

6. Any history of clinically significant haematologic abnormality, including coagulopathy or any history of chronic treatment with anticoagulants (e.g. warfarin, etc) or antiplatelet agent (e.g. aspirin, etc)
7. Clinically significant abnormalities in laboratory test results at enrolment and during the screening period (including complete blood count, coagulation, chemistry panel and urinalysis) unless judged not significant by the investigator.
8. Alanine aminotransferase (ALT) or aspartate aminotransferase (AST) level  $\geq 2.5$  times the upper limit of normal (ULN) confirmed during screening period
9. Being pregnant or lactating or have positive serum pregnancy test at enrolment or positive urine pregnancy test during the study
10. Concomitant disease or condition which could interfere with the conduct of the study, or for which the treatment might interfere with the conduct of the study, or which would, in the opinion of the investigator, pose an unacceptable risk to the patient in this study, including, but not limited to, cancer, alcoholism, drug dependency or abuse, or psychiatric disease
11. Severe concomitant illness(es) that, in the investigator's judgment, would adversely affect the patient's participation in the study
12. Presence of skin comorbidities that may interfere with study assessments
13. History of cancer: Patients who have had basal cell carcinoma, localized squamous cell carcinoma of the skin, or in situ carcinoma of the cervix are eligible provided that the subject is in remission and curative therapy was completed at least 12 months prior to the date informed consent. Patients who have had other malignancies are eligible provided that the subject is in remission and curative therapy was completed at least 5 years prior to the date of informed consent.
14. Patient who has a scheduled in-patient surgery or hospitalization during the study.
15. History of Guillain-Barré syndrome
16. A helminth parasitic infection diagnosed within 24 weeks prior to the date informed consent is obtained that has not been treated with, or has failed to respond to standard of care therapy

17. Positive hepatitis B surface antigen, or hepatitis C virus antibody serology, or a positive medical history for hepatitis B or C. Patients with a history of hepatitis B vaccination without history of hepatitis B are allowed to enrol
18. A history of known immunodeficiency disorder including a positive human immunodeficiency virus (HIV) test
19. Receipt of immunoglobulin or blood products within 30 days prior to the date informed consent is obtained
20. Receipt of any marketed (eg omalizumab) or investigational biologic within 4 months or 5 half-lives prior to randomization is obtained, whichever is longer
21. Treatment with an investigational drug within 8 weeks or within 5 half-lives (if known), whichever is longer, before the baseline visit
22. Any allergen immunotherapy within 4 months prior to or throughout the study.
23. Having used any of the following treatments within 4 weeks before the Day -2 baseline visit, or any condition that, in the opinion of the investigator, is likely to require such treatment(s) during study:
  - a. Immunosuppressive/immunomodulating drugs (eg, systemic corticosteroids, cyclosporine, mycophenolate-mofetil, IFN- $\gamma$ , Janus kinase inhibitors, azathioprine, methotrexate, etc.)
  - b. Phototherapy for AD
24. Any cell-depleting agents including but not limited to rituximab: within 6 months before the baseline visit, or until lymphocyte count returns to normal, whichever is longer
25. Initiation of treatment of AD with prescription moisturizers or moisturizers containing additives such as ceramide, hyaluronic acid, urea, or filaggrin degradation products during the screening period (patients may continue using stable doses of such moisturizers if initiated before the screening visit)
26. Regular use (more than 2 visits per week) of a tanning booth/parlor within 4 weeks of the baseline visit
27. Active chronic or acute infection requiring treatment with systemic antibiotics, antivirals, antiparasitics, antiprotozoals, or antifungals within 2 weeks before the baseline visit, or superficial skin infections within 1 week before the baseline visit. NOTE: patients may be rescreened after infection resolves

28. Known or suspected history of immunosuppression, including history of invasive opportunistic infections (eg, histoplasmosis, listeriosis, coccidioidomycosis, pneumocystosis, aspergillosis) despite infection resolution: or unusually frequent, recurrent, or prolonged infections, per investigator judgment
29. Planned or anticipated major surgical procedure during the patient's participation in this study
30. Receipt of live attenuated vaccines 30 days prior to the date of randomization. Receipt of inactive/killed vaccinations (eg, inactive influenza) are allowed provided they are not administered within 1 week before/after any IP administration.
31. Patient is a member of the investigational team or his/her immediate family
32. Pregnant woman
33. Previously received benralizumab (MEDI-563)

### **Investigational product**

Benralizumab 30 mg or placebo solution for injection will be administered SC every month, for 3 doses. Subjects will be randomized in a 1:1 ratio. The IP will be administered at the study centre on treatment visits on study days 0, 28 and 56 ( $\pm$  3 days). The placebo will have an appearance identical to that of drug. Those administering treatment, any study staff involved in subject evaluations, and the subjects, will remain blinded to treatment assignment for the duration of the study.

### **Investigational product administration**

The IP will be administered by a study physician. For WOCBP urine pregnancy test will be done; IP will be administered only when the result of the test is negative. The site of injection of the IP is rotated such that the patient receives IP at a different anatomical site at each treatment visit. The injection site will be recorded at each treatment visit. After IP administration the subject should be observed for a minimum of 2 hours for the appearance of any acute drug reactions.

## **Efficacy Endpoints**

### *Primary endpoint*

1. The number of eosinophils per millimetre squared of skin, measured 24 hours post intradermal allergen challenge, 65 days after the first dose. The number of eosinophils in the skin will be assessed by histological examination of a punch skin biopsy obtained from the site of the intradermal allergen challenge.

### *Secondary endpoints*

1. The number of basophils per millimetre squared of skin, measured 24 hours post intradermal allergen challenge, after 65 days of dosing. The number of basophils in the skin will be assessed by immunohistochemistry of a punch skin biopsy obtained from the site of the intradermal allergen challenge, using a commercial antibody specific for basophils.
2. The size of the late cutaneous response, measured 24 hours post intradermal allergen challenge, 65 days after the first dose. The late cutaneous response will be calculated using the length and width of the wheal and flare response to a standardized amount of allergen extract.
3. Eczema Area and Severity Index (EASI) score.

### *Exploratory endpoints*

1. The number of eosinophils, basophils, eosinophil progenitors, ILC2s, CD4+ T cells and hemopoietic cells in skin lesions after 28 days of dosing. The number of cells in skin lesions will be assessed by flow cytometry following digestion of the biopsy and staining with a validated panel of antibodies.

## **Safety Endpoints**

Blood and urine will be evaluated during screening for study eligibility, and at follow up to determine safety.

## **Safety Variables**

### *Adverse Events*

An AE is defined as any untoward medical occurrence in a clinical investigation subject who receives a pharmaceutical product at any dose, whether or not there is a causal relationship with the investigational treatment. An AE could therefore be any unfavorable or unintended sign (including abnormal laboratory findings), symptom, or disease temporally associated with the use of a medicinal product, whether or not considered related to the medicinal product. This definition includes intercurrent illnesses or injuries and exacerbation of pre-existing conditions. An unexpected AE is an AE not identified in nature, severity, or frequency in the current Investigator Drug Brochure.

The investigator will rate the intensity of AEs according to the following categories.

- Mild = symptoms or signs present; no limitation of activities; no medical intervention required.
- Moderate = some limitation of activities; no or minimal medical intervention required.
- Severe = marked limitation of activities; medical intervention required, possible including hospitalization.

Serious adverse events will be collected for the duration of the study. All AEs will be monitored until resolution or, if the AE is determined to be chronic, until stable. If an AE remains unresolved at the conclusion of the study, a clinical assessment will be made by the investigator and medical monitor to determine whether continued follow-up of the AE is warranted.

### *Serious Adverse Events*

Serious AEs and AEs listed in the drug investigator brochure will be considered expected events. See the Investigator Drug Brochure for additional details of drug expected AEs.

The relationship of the study treatment to an AE will be determined by the investigator based on the following definitions:

- Not related  
The subject was not exposed to drug, or another cause is obvious.
- Probably not related  
The AE is more likely explained by another cause, and the time of occurrence of the AE is not reasonably related to drug administration.
- Possibly related  
The drug administration and the AE occurrence were reasonably related in time, and the AE is explained equally well by causes other than drug; or drug administration and the AE were not reasonably related in time, but the AE is not obviously a result of other causes.
- Probably related  
The drug administration and the AE occurrence were reasonably related in time, and the AE is more likely explained by drug exposure than by other mechanisms.

An SAE is defined as any untoward medical occurrence that:

- Results in death.
- Is life threatening (*i.e.*, the subject was, in the opinion of the investigator, at immediate risk of death from the event as it occurred).
- Requires or prolongs hospitalization.
- Results in persistent or significant disability or incapacity (*i.e.*, the event causes a substantial disruption of a person's ability to conduct normal life functions).
- Is a congenital anomaly or birth defect in the offspring of the treated subject.
- Is an important and significant medical event that, based upon appropriate medical judgment, may jeopardize the subject or may require medical or surgical intervention to prevent one of the other outcomes defining SAE.

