## **Safety Reporting**

The study drug, benralizumab, is an off-label indication for subjects recruited for this study. The Principal Investigator will therefore submit expedited reports, as indicated/necessary for reporting of serious adverse drug reactions, by fax, directly to Health Canada Biologics and Genetic Therapies Directorate.

Adverse drug reactions that are *both serious and unexpected* are subject to expedited reporting to Health Canada. Expedited reporting of reactions which are serious but expected is not required. Expedited reporting is not required for serious events from clinical investigations that are considered unrelated to the study product, whether or not the event is expected.

In accordance with Health Canada requirements, an Adverse Drug Reaction Report will be filed in the cases

- where the adverse drug reaction is neither fatal nor life-threatening, within 15 days after becoming aware of the information;
- where adverse drug reactions is fatal or life-threatening, immediately where possible and, in any event, within 7 days after becoming aware of the information;
- within 8 days after having informed Health Canada of the adverse drug reactions, submit as complete as possible, a report which includes an assessment of the importance and implication of any findings

All safety reports submitted to Health Canada will also be submitted to AstraZeneca at the following address: [[contact]](mailto:[contact]).

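### The protocol's rule for expected events does not agree with its definition of an unexpected event, so some serious drug-related reactions could miss expedited reporting

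*Combined protocol and SAP*

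**What the plan says.** Three sections of the combined protocol and SAP bear on the point.

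- **Adverse Events** defines unexpectedness by comparison with the brochure: "An unexpected AE is an AE not identified in nature, severity, or frequency in the current Investigator Drug Brochure". Seriousness plays no part in this definition.
- **Serious Adverse Events** opens with a rule for the opposite category: "Serious AEs and AEs listed in the drug investigator brochure will be considered expected events". It then refers the reader to the brochure for further detail, without asking that severity or frequency match.
- **Safety Reporting** uses the classification. Drug reactions that are serious and also unexpected "are subject to expedited reporting to Health Canada". For the rest, "Expedited reporting of reactions which are serious but expected is not required". Serious events judged unrelated to the product are exempt as well.

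The clocks are, for a fatal or life-threatening reaction, "immediately where possible and, in any event, within 7 days after becoming aware of the information", and otherwise "where the adverse drug reaction is neither fatal nor life-threatening, within 15 days after becoming aware of the information". The manufacturer is reached through the same channel: "All safety reports submitted to Health Canada will also be submitted to AstraZeneca".

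**The concern.** Expected and unexpected should be complements: every event falls in exactly one class, by one test. Here the two classes are defined in different sections by different tests. One compares three attributes of the event with the brochure. The other asks only whether the event is listed, or, on a broader reading, only whether it is serious. No section gives either rule precedence.

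This would be a drafting blemish if nothing depended on it, but the classification decides whether a serious drug reaction goes out as an expedited report. The Safety Reporting section describes the use in this trial as off-label and has the Principal Investigator report directly to Health Canada, so the protocol's wording guides the person who classifies the event. The conflicting sentence also stands first under the heading where staff would look when handling a serious event.

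**Working it through.** No arithmetic applies, and the plan gives no figure to reproduce. The check is to apply each reading of the two rules and see whether they can classify the same event differently.

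**Readings of the sentence in Serious Adverse Events**

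- *Narrow:* the phrase about being listed qualifies both nouns. Any listed event, serious or not, is expected.
- *Broad:* the phrase qualifies only the second noun. All serious events are expected, and so are all listed events.

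**Readings of the definition in Adverse Events**

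- *Ordinary:* a departure from the brochure in any one of nature, severity or frequency makes the event unexpected.
- *Loose:* the event is unexpected only if none of the three is identified in the brochure.

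**The four combinations**

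| Serious Adverse Events sentence | Adverse Events definition | Serious drug-related reactions classified differently by the two sections |
|---|---|---|
| Narrow | Ordinary | Those listed, but more severe or more frequent than described |
| Narrow | Loose | None |
| Broad | Ordinary | All that depart from the brochure in nature, severity or frequency |
| Broad | Loose | Those not listed at all |

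The rules agree in one combination of four. That one requires the loose definition, under which a known type of reaction at unprecedented severity would not be unexpected. The words severity and frequency would then do almost no work.

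**Which events the reporting rule could miss**

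1. The event must be serious, because non-serious events never qualify for these reports.
2. It must be considered drug-related, because unrelated serious events are exempt whatever their expectedness.
3. On the narrow reading it must be listed in the brochure, because an unlisted event is unexpected under both rules.
4. It must exceed the brochure's description in severity or frequency, because otherwise both rules call it expected.

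For an event that meets all four conditions, the Serious Adverse Events sentence leads to no expedited report, while the Adverse Events definition leads to a report within 7 or 15 days. Forwarding to the manufacturer is stated only for reports sent to Health Canada, so it follows the same branch.

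**The case against.** The best defence is that the narrow reading is plainly the intended one and that, so read, the sentence is shorthand for the fuller definition one section earlier. The referral to the brochure straight after it supports this. So does the Safety Reporting section, which sets clocks for serious unexpected reactions and deals separately with serious expected ones, so both kinds must be able to exist. The sentence does not say that listing settles the matter whatever the severity or frequency. An investigator who read both sections together could treat an event worse than described as unexpected. Filing is also tied to Health Canada requirements.

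Much of this stands. A reader might infer that the plan makes every serious event expected, so that the expedited trigger could never be met. The broad reading would have that effect, but the Safety Reporting section shows that it was probably not meant.

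Three other inferences also go too far:

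- *That a listed mild event which becomes serious is enough to show the conflict.* The protocol grades intensity separately from seriousness, which it defines largely by outcome. The two rules differ only if the event also exceeds the brochure in severity or frequency.
- *That every listed event exceeding its description would drop out of the reports.* Only serious, drug-related reactions were ever candidates, and they may be misclassified; the documents do not show that they will be.
- *That affected reactions would go unrecorded.* Serious events are collected for the duration of the study, and all adverse events are followed until resolved or stable, whatever their expectedness.

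The defence does not remove the narrow conflict. The shorthand omits two of the three attributes in the definition it is said to abbreviate, and nothing says that the fuller version prevails. An investigator who applied the sentence as it stands would be following the protocol.

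**Conclusion.** The point holds in limited form. The two rules are inconsistent, and on the likely intended reading the inconsistency affects serious, drug-related reactions that are listed in the brochure but exceed its description in severity or frequency. The conclusion rests on the ordinary reading of the definition of unexpected; combining the loose reading with the narrow reading of the sentence would remove the conflict.

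Its size in events cannot be stated. It depends on what the brochure lists and whether it gives severity and frequency, and the brochure is not part of the documents. With 20 evaluable subjects planned, few events may be involved. The randomisation, sample size and primary analysis are untouched. The sentence still deserves correction, because a written rule that can steer a serious reaction away from a 7- or 15-day report is more than a matter of style.

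**What to change.** Reconcile the Serious Adverse Events section with the Adverse Events section so that one definition governs. One way is to replace the opening sentence of Serious Adverse Events with: *An AE, serious or not, is expected only if its nature, severity and frequency are consistent with the current Investigator Drug Brochure; all other AEs are unexpected.* This makes the two classes complementary and closes off the misreading that all serious events are expected. The Safety Reporting section can stay as it is.

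The cost is one sentence of protocol text and possibly a few more expedited reports. No trial procedure or analysis changes.
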